11.7.4.6 Hy's Law

Hepatic function abnormality defined by an increase in AST and/or ALT to $\geq 3 \times$ ULN concurrent with an increase in total bilirubin to $\geq 2 \times$ ULN but without increase in alkaline phosphatase (i.e., alkaline phosphatase $< 2 \times$ ULN) meets the criteria for Hy's Law and raises the concern for drug-induced liver injury when no other cause of the abnormal laboratory results is identified.

A figure displaying patients who are at risk for a drug induced liver injury according to Hy's law will be presented. A listing of patients at risk will also be presented.

11.7.5 Vital Signs

Clinically significant findings noted during screening will be reflected on the medical history CRF, while those noted during study treatment will be collected on the AE CRFs. The following vital signs will be summarized: pulse rate (beats/min), systolic blood pressure (SBP; mmHg), diastolic blood pressure (DBP; mmHg), body temperature (C), Height (cm) and weight (kg). Height will be recorded at screening only.

Vital signs and change from baseline will be summarized. All vital signs and change from baseline through the last Cycle will be summarized by cohort and all cohorts combined. This will include a summary of the maximum and minimum values observed while the patient was on treatment and change from baseline to that observed value.

Potentially clinically important vital sign results will be summarized separately. These criteria are defined as increases in blood pressure and weight changes:

- SBP (≥ 160 mmHg, ≥ 180 mmHg, ≥ 200 mmHg)
- DBP (≥ 100 mmHg, ≥ 120 mmHg)
- Weight increased $\geq 5\%$ from baseline
- Weight decreased $\geq 10\%$ from baseline

All vital signs will be listed.

11.7.6 Physical Examinations, ECGs, and Other Observations Related to Safety

11.7.6.1 Physical Examination

A physical examination including all major body systems is mandated at Screening and End of Treatment Visits only. During study treatment, symptom-directed physical examinations are performed.

Complete physical examinations will be conducted during screening and at the End of Treatment visit. Abbreviated physical examinations will be performed on Day 1 and Day 15 of all cycles. Any new abnormal physical exam findings will be collected as AEs. Physical Examination data will be listed for the Safety population

11.7.6.2 Eye Exam (Cohort 9 only)

Patients with recent ocular complaints (within ≤ 3 months of screening) must have a complete eye examination at Screening Visit performed by a qualified ophthalmologist or optometrist, including but not limited to: uncorrected, corrected and best corrected visual acuity, slit lamp, tonometry examination, and dilated fundus examination. Prior ophthalmologic exam done within 3 months of screening is acceptable provided there are no new symptoms since that exam. End of Treatment Visit slit lamp examinations are required for all patients who experience corneal adverse events during the study and must be performed ≥ 28 days from last dose of enfortumab. Additional eye examinations are to be conducted as clinically indicated.

Eye exam data will be presented as Listings including values obtained on visual acuity tests within 3 months of screening, and End of Treatment Visit (as applicable), and any additional eye measurements (as needed), and corneal Adverse Events.

Eye exam Table will include patient id, baseline visual acuity values, change in visual acuity value by test, and percent change of visual acuity test value till End of Treatment.

Another eye exam Table will include Number of Corneal Adverse Events (absolute and by percentage) by Cohort and for Total.

11.7.6.3 Electrocardiograms

Single and triplicate 12-Lead electrocardiogram (ECG) parameters will be collected. The following will be assessed: rhythm (sinus or other), heart rate (bpm), QRS, QT, RR, and the investigator interpretation. The QT interval corrected for heart rate by the Fridericia's formula (QTcF) will be manually calculated in the database.

A summary of ECG parameters including heart rate (beats/min), QT interval (msec), QTcF (msec), rhythm, and RR interval (msec) and change from baseline will be presented for each planned visit as well as the minimum, maximum, and last observation on-treatment.

For each planned visit for which a triplicate ECG is obtained, the average the 3 values should be calculated for each parameter at each timepoint. The average values will be used for the ECG tables.

The baseline to be used in the calculation of changes over time will be the mean of the 6 pre-dose values, i.e., the triplicate values at -1 hour and -0.5 hours pre-dose.

In addition, listings and summaries will be generated for patients by Maximum ICH E14 Category with QTcF increased to value ≥ 480 and < 500 msec, and value ≥ 500 msec, and patients with change from baseline QTcF increased by ≥ 30 to < 60 msec, and by ≥ 60 msec. Patients with PR value > 220 msec and change from baseline $> 25\%$ as well as patients with QRS > 110 msec and change from baseline $> 25\%$ will also be summarized and presented in Listings. A shift from baseline to worst CTCAE grade summary will also be presented.

A shift from baseline to worst CTCAE (v5.0) grade for QTcF values will also be presented.

QTcF will be graded per CTCAE v5.0. the grades are as follows:

- Grade 0: value < 450 msec
- Grade 1: value 450 to 480 msec
- Grade 2: value > 480 to 500 msec
- Grade 3: value > 500 or increase from baseline > 60 msec

Descriptive summaries for patients meeting the following ECG thresholds (based on the average of triplicate measurements at each time point), will also be provided:

- Absolute QTc ≤ 450 msec, > 450 to ≤ 480 msec, > 480 to ≤ 500 msec, > 500 msec
- Change from baseline QTc ≤ 30 msec, > 30 to ≤ 60 msec, > 60 msec
- PR > 220 msec and change from baseline $> 25\%$
- QRS > 110 msec and change from baseline $> 25\%$

A separate listing of the ECG results along with the overall interpretation will be presented.

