- If the H₂A/antacid is taken twice daily, and sitravatinib is administered in the evening: take the H₂ antagonist or antacid in the morning, wait at least 6 hours (and fast for at least 2 hours) before taking sitravatinib, then take the evening dose of H₂A/antacid at least 1 hour after sitravatinib.

Medications with QTc Prolonging Activity: The risk of QTc prolongation in patients receiving sitravatinib has not been characterized. Use of medications known to prolong QTc and pose risk of Torsades de Pointes (examples listed in [Appendix 3](#)) is to be avoided. Use of medications with conditional risk of Torsades de Pointes should be used with caution during sitravatinib treatment (examples listed in [Appendix 3](#)).

P-gp and BCRP transporters with Sitravatinib: Sitravatinib is a strong inhibitor of P-gp and BCRP transporters (Section 1.3.2). Concomitant medications that are sensitive substrates or substrates with narrow therapeutic index for these transporters (examples listed in [Appendix 3](#)) should be used with caution during sitravatinib treatment.

Strong P-gp Inhibitors with Enfortumab: Concomitant use of enfortumab and medications that are strong inducers/inhibitors of P-gp may affect exposure to MMAE and are prohibited (examples listed in [Appendix 10](#)). Whereas no clinical studies evaluating the drug-drug interaction potential of enfortumab have been conducted, in vitro studies indicate that monomethyl auristatin E (MMAE), the payload component of enfortumab, is a substrate of P-gp ([PADCEV US Prescribing Information](#)).

CYP3A4 Substrates with Sitravatinib: In vitro data imply that sitravatinib is a strong direct inhibitor of CYP3A4 (Section 1.3.2). Concomitant medications that are sensitive substrates or substrates with narrow therapeutic index for CYP3A4 (examples listed in [Appendix 3](#)) should be used with caution during sitravatinib treatment.

Strong CYP3A4 Inhibitors with Enfortumab: Concomitant use of enfortumab with a strong CYP3A4 inhibitor may increase free MMAE exposure, which may increase the incidence or severity of enfortumab toxicities ([PADCEV US Prescribing Information](#)), and are prohibited (examples listed in [Appendix 10](#)). Whereas no clinical studies evaluating the drug-drug interaction potential of enfortumab have been conducted, in vitro studies indicate that MMAE is a substrate of CYP3A4 ([PADCEV US Prescribing Information](#)).

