- Cohort 8: Patients with documented disease progression on or after a previous anti-PD-(L)1 and ADC (in combination or separately, and in any order), and considered ineligible for platinum-based chemotherapy.

Appendix 9 of the Protocol describes addition of Cohort 9 to evaluate sitravatinib in combination with pembrolizumab and enfortumab. The next section describes the initial lead-in dose escalation followed by further evaluation of clinical activity in 2 populations if a tolerable dose regimen is identified. Cohort 9 is introduced and implemented with this protocol Version 4.0.

- Cohort 9 (including lead-in dose escalation): Patients who have previously received a PD-(L)1 checkpoint inhibitor and a platinum-based chemotherapy.

Table 1 Schedule of Assessments: Cohorts 1 through 8

Assessments	Screen/Baseline	Cycles 1, 2, and 3		≥ Cycle 4		End of Treatment		
	Within 28 days	Day 1 (± 2 days for Cycles 2 & 3)	Day 15 (± 2 days)	Day 1 (± 2 days)	Day 15 (± 2 days)	End of Treatment/ Withdrawal ¹⁴	Post Treatment Follow Up	
Study Participation Informed Consent ¹	Before study specific assessments							
Tumor Tissue Collection for PD-L1 Expression, Immune Cell Populations and Tumor Gene Alterations ²	X ²		X (Cycle 2 only) Optional ²					
Medical History, Disease History, Prior Therapy	X							
ECOG Performance Status	X							
Physical Exam ³	X					X		
Abbreviated Physical Exam ³		X	X	X	X if nivolumab Q2W			
Vital Signs ⁴	X	X	X	X	X if nivolumab Q2W	X		
Pregnancy Test ⁵	X	As clinically indicated						
Hematology ^{6, 7}	X	X	X	X		X		
Coagulation ^{6, 7}	X	As clinically indicated						
Urinalysis ^{6, 7}	X	As clinically indicated						
Serum Chemistry ^{6, 7}	X	X	X	X		X		
Thyroid Function Test ^{6, 7}	X	X		X		X		
Blood for Sitravatinib Pharmacokinetics ⁸		See Table 2						

Assessments	Screen/Baseline	Cycles 1, 2, and 3		≥ Cycle 4		End of Treatment	
	Within 28 days	Day 1 (± 2 days for Cycles 2 & 3)	Day 15 (± 2 days)	Day 1 (± 2 days)	Day 15 (± 2 days)	End of Treatment/ Withdrawal ¹⁴	Post Treatment Follow Up
ctDNA blood sample ⁹	X	At assessment for confirmation of disease response (PR or CR)				X	
Single 12-Lead ECG ¹⁰	X	As clinically indicated				X	
Triplicate 12-Lead ECG ¹⁰		See Table 2					
Echocardiogram or MUGA	X (Within 35 days)	Cycle 3 only		As clinically indicated after C3		X	
		(± 7 days)					
Disease Evaluation ¹¹	X	Every 8 weeks (± 10 days) for ~12 months					
		and then every 16 weeks					
Sitravatinib Dispensing and/or Reconciliation		X		X			

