- 8 Pharmacokinetic Samples: Blood samples to be collected following ECGs and assessment of vital signs as scheduled in Table 2.
- 9 Blood samples for ctDNA analysis: Blood will be collected in two 10 mL Streck brand Cell-Free DNA Blood Collection tubes allowing shipping and stability at ambient temperatures.
- 10 12-Lead ECGs: Triplicate ECGs will accompany PK sampling as described in Table 2. In addition, ECGs are to be performed as clinically indicated. Assessments will include an evaluation of heart rate, QT, and QTc intervals. RR interval should be recorded during each ECG assessment in order to calculate QTcF.
- 11 Disease Evaluations: To be performed at screening (28-day window allowed) and every 8 weeks from Cycle 1 Day 1 (\pm 10-day window for all other assessments except screening) until week 49 (~12 months) and then every 16 weeks. All on-study disease evaluations should be based on a calendar beginning from the first day of dosing. At screening/baseline, assessments are to include CT with contrast of the chest, CT or MRI of the abdomen and pelvis, as well as brain Magnetic Resonance Imaging (MRI) with and without gadolinium or CT with contrast, a whole-body bone scan (or PET or PET/CT if local standard for clinical trials) and evaluation of any superficial lesions. Subsequent disease assessments should include all sites of disease identified at baseline or suspected to have developed; bone scans may be performed half as often (every 16 weeks) as other radiology evaluations and should be performed during assessment for confirmation of disease response. More detailed guidance on exceptional circumstances is provided in the protocol. Patients who discontinued the study for reasons other than objective disease progression will continue to have disease assessments at the same frequency until patient has radiologically confirmed progression, initiates a new anticancer therapy, or death.
- 12 Adverse Events: Serious Adverse Events (SAEs) will be reported from the time of informed consent until at least 28 days after the last administration of a study treatment. Adverse events will be reported from the first day of study treatment until at least 28 days after last dose of study drug, and until resolution or stabilization of acute adverse events and/or ongoing SAEs.

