- 13 Long Term Follow-up: Survival status and subsequent therapies will be collected during long term follow-up every 2 months (\pm 14 days) from the End of Treatment Visit until death or lost to follow-up. Follow-up may be performed by telephone contact or email.
- 14 End of Treatment: Perform within 7-14 days of decision to permanently discontinue all study treatment. Assessments that have been completed in the previous 4 weeks do not need to be repeated (8 or 16 weeks for tumor assessments in accordance with schedule).

Table 2 Sitravatinib Schedule of PK, Biomarker Samples and Triplicate ECG Assessments: Cohorts 1 through 8

Collection Time and Allowable Window	Screen/ Baseline	Cycle 1 Day 1			Cycle 1 Day 15 (± 2 days)		Cycle 2, 3, 5 Day 1 only	Cycle 2 Day 15 only
		Pre-dose (-0.5-0 hour)	30 min (± 10 min)	7 hour ⁵ (5-9 hour)	Pre-dose (-0.5-0 hour)	7 hour ⁵ (5-9 hour)		
PK Sample ^{1,2}	Within 28 days	X	X	X	X	X	X	
TCR Sequencing ³		X			X			
Flow Cytometry ³	X	X			X			X
Protein and Cytokine Biomarkers ³		X			X			X
Triplicate ECG ⁴		X (-1 hour)	X (-0.5 hour)	X	X	X	X	

- Scheduled vital signs and triplicate ECGs precede PK sample collection in all cases. Sitravatinib dosing and sampling should precede nivolumab infusion. Post-dose PK sample collections are not required for visits where sitravatinib dose is held but should be subsequently collected at the next visit following at least 7 days of sitravatinib intake. Alternatively, both pre-dose and post-dose PK collections are not required for visits preceded by more than 4 days of sitravatinib hold but should be subsequently collected at the next visit following at least 7 days of sitravatinib intake.
- In addition to the scheduled samples, an unscheduled PK blood sample should be drawn before a daily sitravatinib dose (trough sample) in the event of any of the following events: 1) as soon as possible after an SAE, 2) at a clinic visit at least one week following a dose modification of the investigational agent, and 3) as soon as possible after renal function declines by one Stage as defined in Appendix 2 of the Protocol, if the patient continues study treatment.
- The Day 1 blood samples for TCR sequencing, flow cytometry, protein and cytokine biomarker studies may be drawn up to 2 hours before dosing. The screen/baseline sample should not be collected on the same day as the pre-dose Cycle 1 Day 1 sample.

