- 15 Eye exam: Patients with recent ocular complaints (within ≤ 3 months of screening) must have a complete eye examination at Screening Visit performed by a qualified ophthalmologist or optometrist, including but not limited to: uncorrected, corrected and best corrected visual acuity, slit lamp, tonometry examination, and dilated fundus examination. Prior ophthalmologic exam done within 3 months of screening is acceptable provided there are no new symptoms since that exam. End of Treatment Visit slit lamp examinations are required for all patients who experience corneal adverse events during the study and must be performed ≥ 28 days from last dose of enfortumab. Additional eye examinations are to be conducted as clinically indicated.

Table 4 Sitravatinib Schedule of PK, Biomarker Samples and Triplicate ECG Assessments: Cohort 9

Collection Time and Allowable Window	Screen/ Baseline	Cycle 1 Day 1			Cycle 2 Day 1 (± 2 days)		Cycle 2, 3, 6 Day 8 only	Cycle 3 Day 1 only
	Within 28 days	Pre-dose (-0.5-0 hour)	30 min (± 10 min)	7 hour ⁵ (5-9 hour)	Pre-dose (-0.5-0 hour)	7 hour ⁵ (5-9 hour)	Pre-dose (-0.5-0 hour)	Pre-dose (-0.5-0 hour)
PK Sample ^{1,2}		X	X	X	X	X	X	
TCR Sequencing ³		X			X			
Flow Cytometry ³	X	X			X			X
Protein and Cytokine Biomarkers ³		X			X			X
Triplicate ECG ⁴		X (-1 hour)	X (-0.5 hour)	X	X	X	X	

- 1 Scheduled vital signs and triplicate ECGs precede PK sample collection in all cases. Sitravatinib dosing and sampling should precede nivolumab infusion. Post-dose PK sample collections are not required for visits where sitravatinib dose is held but should be subsequently collected at the next visit following at least 7 days of sitravatinib intake. Alternatively, both pre-dose and post-dose PK collections are not required for visits preceded by more than 4 days or sitravatinib hold but should be subsequently collected at the next visit following at least 7 days of sitravatinib intake.
- 2 In addition to the scheduled samples, an unscheduled PK blood sample should be drawn before a daily sitravatinib dose (trough sample) in the event of any of the following events: 1) as soon as possible after an SAE, 2) at a clinic visit at least one week following a dose modification of the investigational agent, and 3) as soon as possible after renal function declines by one Stage, if the patient continues study treatment.

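### One QTc outlier table in the SAP is tied to triplicate averages, so single ECGs (clinically indicated or End of Treatment) cannot enter it on a literal reading; the other QTc displays do not say whether they enter, and category boundaries conflict at exact values

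*SAP*

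**What the plan says.** SAP 11.7.6.3 (Electrocardiograms) says that both single and triplicate ECGs are collected. For a planned visit with a triplicate, the three values are averaged, and then: "The average values will be used for the ECG tables". Five kinds of QTc display follow:

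- ECG parameters and change from baseline by planned visit, with the minimum, maximum and last on-treatment value.
- Listings and summaries of "patients by Maximum ICH E14 Category with QTcF increased to value" from 480 to below 500 msec, or 500 msec and above, and of changes from 30 to below 60 msec, or 60 msec and above.
- A shift from baseline to worst CTCAE grade for QTcF.
- A threshold summary, introduced by "Descriptive summaries for patients meeting the following ECG thresholds (based on the average of triplicate measurements at each time point), will also be provided".
- A listing of ECG results.

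Only the threshold summary names triplicate averages as its basis.

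On timing, the last triplicate column in SAP Table 2 (Cohorts 1-8) is "Cycle 2, 3, 5 Day 1 only". In SAP Table 4 (Cohort 9) the last in time falls under "Cycle 2, 3, 6 Day 8 only". In SAP Tables 1 and 3 the row "Single 12-Lead ECG" covers screening, clinically indicated ECGs and End of Treatment. Footnote 10 to those tables adds: "In addition, ECGs are to be performed as clinically indicated".

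**The concern.** Protocol 5.7.1 says: "The risk of QTc prolongation in patients receiving sitravatinib has not been characterized". ECGs taken because a problem is suspected are the ones most likely to show prolongation, and those ECGs are single. A table confined to triplicate averages has no place for them, nor for the End of Treatment ECG. It could report no patient above 500 msec while the listing shows one.

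A second weakness is that two summaries of the same endpoint place the same boundary value in different categories, so their counts can disagree without any error in the data.

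**Working it through.** **1. When scheduled triplicates end.** Nominal day = (cycle - 1) x cycle length + day. Cycle lengths of 28 days (nivolumab cohorts) and 21 days (Cohort 9) come from Protocol 5.1.2.

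- Cohorts 1-8, Cycle 5 Day 1: 4 x 28 + 1 = Day 113.
- Cohort 9, Cycle 6 Day 8: 5 x 21 + 8 = Day 113.

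The visit labels differ but the nominal day is the same.

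**2. What falls outside the threshold summary.** After Day 113 the only ECGs in the schedule are the single End of Treatment ECG and any clinically indicated ones. Clinically indicated single ECGs before Day 113 are outside it as well. SAP 11.7 defines on-treatment as running to 28 days after the last dose or the start of subsequent anti-cancer therapy, whichever is earlier. The End of Treatment visit is 7-14 days after the decision to stop (SAP Table 1, footnote 14), so its ECG will usually be on-treatment safety data. The literal loss is therefore one scheduled on-treatment ECG per patient, plus every clinically indicated one.

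**3. Whether the other displays state a rule.** The ICH E14 summary, the worst-grade shift and the minimum/maximum/last summary name no restriction to triplicates, but neither do they say that single or unscheduled ECGs enter. The laboratory shift tables (SAP 11.7.4, 11.7.4.1 and 11.7.4.2) expressly include unscheduled visits in the worst value. The ECG section has no equivalent wording. PR and QRS outliers appear twice with the same criteria, once with no stated basis and once on triplicate averages.

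**4. Boundary values under each set of categories (msec).**

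| Value | Threshold summary | ICH E14 summary | SAP CTCAE grade |
|---|---|---|---|
| QTc 450 | ≤450 | no category | Grade 1 |
| QTc 480 | >450 to ≤480 | ≥480 to <500 | Grade 1 |
| QTc 500 | >480 to ≤500 | ≥500 | Grade 2 |
| Change 30 | ≤30 | ≥30 to <60 | not graded |
| Change 60 | >30 to ≤60 | ≥60 | not Grade 3 on change (needs >60) |

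Values of 449, 451, 479, 481, 499 and 501, and changes of 29, 31, 59 and 61, fall in matching categories. The conflict is confined to the exact values in the table. The threshold summary agrees with the CTCAE grades at 480, 500 and a change of 60, but not at 450. The ICH E14 summary disagrees with them at 480, 500 and a change of 60.

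**5. Illustration.** Take a QTcF of 510 msec on a symptom-prompted single ECG. It is absent from the threshold summary. It counts as ≥500 in the ICH E14 summary and as Grade 3 in the shift only if the programmer admits single ECGs to those tables. It appears in the listing.

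**The case against.** The strongest reply is that the threshold summary is only one of several displays. A reader might infer that the SAP has no table in which late or symptom-prompted prolongation can appear. The documents do not support that: nothing in 11.7.6.3 bars a single ECG from the ICH E14 summary, the worst-grade shift, the on-treatment extremes or the listing. This part of the reply stands.

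The parenthesis can also be read as an averaging instruction (where a triplicate exists, use its mean) rather than as an exclusion. The general averaging rule is worded that way, since it applies to planned visits with a triplicate. On that reading the defect is an unstated rule. It still needs repair, because two programmers could produce different counts from the same text.

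A reader might also size the gap by the share of treatment time after Day 113. That would measure how sparse the ECG schedule is, not how many recorded ECGs the SAP discards, so it is not a measure of impact.

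Nor do the two summaries use different thresholds. Where they overlap the numbers are the same (480, 500, 30, 60). They differ in which side includes the boundary value, and the ICH E14 summary has no 450 category.

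Finally, Protocol 9.5.3 plans an exposure-response analysis of QTc change, for which PK-paired triplicates are the natural data. That supports keeping triplicate averages for mean change. It gives no reason to leave single readings out of an outlier count.

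**Conclusion.** The concern holds in limited form. One QTc outlier table, read literally, cannot show prolongation found on clinically indicated or End of Treatment ECGs, and the tables that could show it do not say that they will. Its boundaries conflict with the ICH E14 summary at four exact values and with the SAP's CTCAE grades at one.

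The data are not lost, because the listing holds them. The documents give no count of single ECGs or of how many would exceed a threshold, so the effect on the tables cannot be quantified. The conclusion assumes that clinically indicated ECGs are taken as single readings, as the schedule sets out, and that the parenthesis means what it literally says. If it is only an averaging instruction, what remains is the missing rule and the boundary conflict. For a safety question that the protocol itself calls uncharacterised, this is worth settling in the SAP amendment that precedes database lock.

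**What to change.** - Replace the ICH E14 and threshold summaries by one categorical outlier summary built from all on-treatment ECGs. Use the triplicate average where there is one and otherwise the single value, and flag outliers that rest on a single reading. Specify PR and QRS once, on the same basis.
- Use one set of boundaries. For absolute QTcF take the SAP's CTCAE grades: below 450, 450 to 480, >480 to 500, >500. A cut at >450 would not match, because the SAP's Grade 1 starts at 450. For change use >30 and >60; the latter matches the SAP's Grade 3 and the former is not graded.
- State that the worst-grade shift includes unscheduled and End of Treatment ECGs, as the laboratory section does for unscheduled visits.
- Keep triplicate averages for the by-visit mean change.

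The cost is SAP wording and a small programming change, with no new data. The downside is noise: a single reading is less precise than an average of three, and its change is taken against a baseline that averages six readings. A few more outliers may appear, and the flag lets a reader separate them.
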